### **Recruitment and Retention**

It is anticipated that 120 participants can be recruited within 48 months based on prior rates of enrollment for alcohol studies conducted by the proposed study team and the awareness that the

current proposal will study individuals over a longer period of time and needs to recruit a minimum number of individuals with heavy drinking and with high anxiety. In our recently completed placebo study of baclofen we were able to recruit 80 subjects over 19 months with 75% trial retention. Retention is an important objective of the trial with our target being a minimum of 75% of subjects completing the trial. Medical Management and the regular meetings with our research coordinator during study visits have proven useful in encouraging retention and compliance with medication and we have averaged 75-85% retention for most trials.

### **Medical Management Intervention**

The psychosocial treatment for the proposed study will be Medical Management (MM) (Pettinati et al, 2005)). [name] will be primarily responsible for MM with [name] providing back-up. [name] and [name] have been trained and certified in MM by [name] of the University of Pennsylvania. MM is designed as a means for physicians and other health care providers to encourage individuals with AD to make progress towards their drinking goals of reduction or abstinence and to encourage compliance with medication. MM does not provide intense counseling methods for reducing drinking or dealing with relapse triggers which is thought to be an advantage for medication trials as MM does not overpower a possible medication effect.

### **Baclofen Blood Level Analyses**

Baclofen trough plasma levels will be measured at week 4 at 8 hours after a dose in all participants. Trough levels will be one measure of compliance and can help to determine if some participants have unusually high exposures that could be associated with adverse events

### **Enantiospecific assay of baclofen in plasma and urine.**

A wide range of assays have been employed for baclofen analysis, with a summary of enantiospecific methods provided by Goda et al. (2004). Though Goda and others have employed chiral columns or chiral mobile phases to resolve R- and S-baclofen, the indirect approach will be employed here due to its use of robust C18 columns and reduced cost. Bhushan and Kumar (2008) demonstrated that Marfey's reagent, often used for d,l-amino acid resolution allows easy separation of baclofen enantiomers on reversed phase LC after derivatization. Baclofen will be extracted from plasma (0.10 ml) or urine (0.10 ml) by SPE (Spahn 1988), dried thoroughly, then derivatized with Marfey's reagent (1-fluoro-2,4-dinitrophenyl-5-L-alanine amide, available from Pierce/ThermoFisher) as described previously (Bhushan and Kumar, 2008), then the sample injected on LC (C18). The use of Marfey's reagent permits detection at 340 nm using UV absorbance which should be sufficient for the analysis of baclofen in plasma or urine since peak concentrations in plasma often are in the ?g/ml range. Should additional sensitivity or selectivity be needed, LC-ESI-MS/MS with an AB Sciex 3000 mass spectrometer is available for use. Validation of the LC method for the analysis of baclofen enantiomers will be done following rigorous methods as outlined within FDA guidances (FDA, 2001)

### **Post-Treatment Follow-up**

One month following termination or treatment completion, the study coordinator will call each participant, conduct a TLFB interview, and inquire about general health and adverse events.

Subject participation should average around 21 weeks including screening, randomization, the active medication phase and the one month follow-up. Variations will occur for individual subjects depending upon their schedule, missed visits, etc.

Table 1 Study Schedule of Assessments

	Screen Visit	Initial Visit	Wk 1	Wk 2	Wk 3	Wk 4	Wk 6	Wk 8	Wk 10	Wk 12	Wk 14	Wk 16
Informed consent	X											
Physical/Neuro exam	X											X
Pregnancy testing	X #					X †		X †		X †		X †
CBC & chemistries	X					X*		X*		X*		X*
Baclofen Trough Level						X						
CDT Level	X											X
Archived blood sample	X											
Urinalysis/ toxicology	X											X**
M.I.N.I./SCID	X											
DrInC, FMAST	X											
STAI Y-1 (State)	X	X	X	X	X	X	X	X	X	X	X	X
STAI Y-2 (Trait)	X											X
CIWA		X										
Sleep Survey	X	X				X		X		X		X
URICA	X											
Vital signs	X	X	X	X		X	X	X	X	X	X	X
Dispense Baclofen/placebo		X	X		X	X	X	X	X	X	X	
Adverse events		X	X	X	X	X	X	X	X	X	X	X
Concomitant meds	X	X	X	X	X	X	X	X	X	X	X	X
Breathalyzer	X	X	X	X	X	X	X	X	X	X	X	X
TLFB	X	X	X	X	X	X	X	X	X	X	X	X
PACS	X	X	X	X	X	X	X	X	X	X	X	X
MM session		X	X	X	X	X	X	X	X	X	X	X

# Serum pregnancy test, \*\* or early termination \* Creatinine, glucose, AST, ALT, GGT, and bilirubin only; †Urine Pregnancy Test only;

\*\*Urinalysis only. Questionnaires: Alcohol/Substance Use Disorders Module (SCID); Alcohol Dependence Scale (ADS); Drinker's Inventory of Consequences (DrInC); Timeline Followback interview (TLFB) F-MAST Family Assessment Scale, the University of Rhode Island Change Assessment Scale (URICA), Penn Alcohol Craving Scale (PACS).

## 7 Statistical Plan

### 7.1 Sample Size Determination

Aim 1. Our power calculations are based on the summary scores over the 12 weeks of treatment (%HDD and %ABST). Under our modified design, we must consider our 3 group design. We use Cohen's (1988) effect size definition for standardized difference for our continuous outcomes, coupled with the work of Addolorato et al. (2011) as guidelines for our power estimates and anticipated effect sizes. The Addolorato et al. (2011), similar to our design consists of 2 medication groups and a PBO reference reports contrast of incidence rates between the medication arms and PBO. Thresholds of the size of the contrasts, for comparability to the Cohen guidelines, are as defined by Rosenthal (1996) who parallels Cohen's (1988) terminology of small, medium, and larger effects for qualitative indexes such as Odds ratios and Incidence rates. Addolorato et al. (2011) saw a small to medium effect size for the contrast between PBO and 30mg. Similarly they saw a medium to large effect for the contrast between PBO and 60mg. Replicating a small effect size(Cohen's  $d=0.2$  for our outcomes) for the contrast between PBO and 30mg coupled with a large effect size (Cohen's  $d=0.8$  for our outcomes) for the contrast between PBO and 90mg, provides 82.2% power with 120 participants (40/arm) in testing the overall baclofen effect as well as 84.7% power to contrast 30 mg to 90 mg under the assumed effect sizes. We assume seeing a large effect size for the PBO-90mg is reasonable due to the medium-large effect seen by Addolorato et al. (2011) 60mg-PBO contrast. Interpreting the effect size for our outcomes, the PBO-overall medication contrast corresponds to a difference of 12% in %HD/%ABS rate between PBO and pooled medication sample over the 12 week period under an arc-sine transformation of the observed individual rates. The effect sizes for the contrast between medication arms corresponds to a difference of 19% in %HD/%ABS rates. We experienced 16.2% attrition in Garbutt et al (2010); therefore, a slightly larger effect size would be required to provide sufficient power for the overall BAC effect. Assuming an average effect size of 0.55, corresponds to a difference of 13% in %HDD/%ABS rate between BAC and PBO, we will have power of 82.0% to detect a statistically significant baclofen effect while accounting for attrition and 78.1% power to detect a significant difference between medication levels at the 0.6 effect size accounting for attrition.

For Aim 2, our main interest is the moderation effect of pre-treatment drinking rates on the BAC effect during treatment, for which we have some evidence as indicated in our Figure 1. Power calculations of a significant DDD x treatment interaction were implemented through SAS power procedure PROC GLMPOWER. Power derivations depended on an expected effect size, where based on the Addolorato et al. (2002) finding in a sample consisting of more DDD pre-treatment, we expect a large effect for BAC compared to PBO for those(Cohen's  $d > 1$ ), whereas Garbutt et al. (2010) in a sample consisting of lower DDD pre-treatment, found no difference (Cohen's  $d=0$ ). The pattern of this behavior is consistent with Figure 1 where more separation between BAC and PBO is evident in those with higher pre-treatment DDD. To detect this interactive behavior in our proposed design, where we assume an effect size of 1.2 corresponding to a difference of 28% in %HDD/%ABS rates in the Heavy Drinking group, and an effect size of 0 within the non-Heavy drinking group, the study will have 86.7% power to detect a significant interaction between Heavy drinking and BAC assignment. Accounting for 16.2% attrition provides 80.2% power to detect the same effect. Power calculations for the moderation assume 40 per treatment arm, with pre-treatment heavy drinking balanced per arm (20 low and 20 high).

For Aim 3, power is comparable to Aim 1, where we will have 82.2% power to detect a BAC effect for anxiety or an effect size of 0.5 and 82.0% power to detect an effect size of 0.55 while accounting for 16.2% attrition.

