## 7.2 Statistical Methods

**Specific Aim 1. To test the hypothesis that baclofen, 30 mg/d and 90 mg/d, is well tolerated and superior to placebo in enhancing abstinence and reducing heavy drinking days in alcohol dependence and that 90 mg/d is superior to 30 mg/d.**

Summary measures of the proportion of abstinence days/heavy drinking days will be derived from the TLFB for the entire medication period. We will derive weekly drinking measures from TLFB as well to provide information on the impact of time on usage. Descriptive statistics and exploratory graphing will be used to assess the distribution of the data and the need for transformations. In the case of %ABS/%HDD, the arc-sine transformation is quite commonly used.

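### Sections 7.1 and 7.2 state no alpha or sidedness; the Aim 1 and Aim 3 powers reproduce only at one-sided 5% (equivalently two-sided 10%) and fall by about 9 to 11 points at two-sided 5%

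*Combined protocol and SAP*

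**What the plan says.** For Aim 1, section 7.1 assumes standardized differences from placebo of 0.2 for 30 mg and 0.8 for 90 mg. It states that this "provides 82.2% power with 120 participants (40/arm) in testing the overall baclofen effect", and gives 84.7% for 30 mg against 90 mg. Citing 16.2% attrition in an earlier trial, it says that "a slightly larger effect size would be required to provide sufficient power for the overall BAC effect", raises the average effect to 0.55, and reports that "we will have power of 82.0% to detect a statistically significant baclofen effect while accounting for attrition", together with "78.1% power to detect a significant difference between medication levels at the 0.6 effect size accounting for attrition".

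For Aim 2 it assumes an effect of 1.2 in heavy drinkers and 0 in the others, with 20 patients per cell: "the study will have 86.7% power to detect a significant interaction between Heavy drinking and BAC assignment", then "Accounting for 16.2% attrition provides 80.2% power to detect the same effect". For Aim 3 it carries over the Aim 1 figures: "we will have 82.2% power to detect a BAC effect for anxiety" at an effect of 0.5, and 82.0% at 0.55 with attrition.

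Section 7.2 words the Aim 1 hypothesis directionally: baclofen is "superior to placebo in enhancing abstinence and reducing heavy drinking days in alcohol dependence and that 90 mg/d is superior to 30 mg/d". Aim 3 is also worded as superiority. Neither section names an alpha or a one- or two-sided test. The closing paragraph of the Abstract describes power as adequate for the primary hypothesis and for anxiety.

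**The concern.** Without a declared alpha and sidedness, the rule for calling the primary contrasts significant is undefined, and a reader cannot tell what the printed powers mean. Most readers would assume two-sided 5%, and the Aim 1 and Aim 3 powers do not hold at that level.

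Two things are at stake. First, the adequacy claim in the Abstract rests on these figures, and the effect size was raised to 0.55 expressly to keep power sufficient after attrition. Second, a result could be significant under one rule and not under the other, with nothing in the plan to decide. For pooled baclofen against placebo at 40 per arm, that gap covers observed standardized differences from 0.32 to 0.38.

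**Working it through.** **Inputs (all from 7.1).** Effects against placebo are 0.2 and 0.8, so pooled baclofen against placebo is (0.2 + 0.8)/2 = 0.5, and 90 mg against 30 mg is 0.8 − 0.2 = 0.6. There are 40 per arm. Attrition of 16.2% leaves 40 × 0.838 = 33.52 per arm, or 33 rounded down. Section 7.2 says the contrasts use all three arms to estimate the variance, so error df = N − 3.

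**Formula.** Power comes from the noncentral t with ncp = d/SE. SE = √(1/n + 1/(2n)) for pooled baclofen against placebo, and √(2/n) for 90 against 30 mg.

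- Pooled, n = 40: SE = 0.1936, ncp = 0.5/0.1936 = 2.582, df 117.
- 90 vs 30 mg, n = 40: SE = 0.2236, ncp = 0.6/0.2236 = 2.683, df 117.
- Pooled, d = 0.55, n = 33: SE = 0.2132, ncp = 2.580, df 96.
- 90 vs 30 mg, n = 33: SE = 0.2462, ncp = 2.437, df 96.

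| Contrast | Printed | One-sided 5% | Two-sided 5% |
|---|---|---|---|
| Pooled, 40/arm, d 0.5 | 82.2% | 82.18% | 72.60% |
| 90 vs 30 mg, 40/arm, d 0.6 | 84.7% | 84.68% | 75.84% |
| Pooled, 33/arm, d 0.55 | 82.0% | 82.03% | 72.37% |
| 90 vs 30 mg, 33/arm, d 0.6 | 78.1% | 78.09% | 67.47% |

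The shortfalls at two-sided 5% are 9.6, 8.9, 9.6 and 10.6 points. At the unrounded 33.52 per arm the two attrition powers are 82.6% and 78.7% one-sided, and 73.1% and 68.2% two-sided. Aim 3 repeats the pooled figures, so at two-sided 5% it has 72.6% and 72.4%.

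The 2-df omnibus test with means 0, 0.2, 0.8 at 5% gives 91.9%, so it does not explain the printed 82.2%. For these contrasts one-sided 5% and two-sided 10% cannot be told apart.

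**Between the rules.** Critical t at df 117 is 1.658 (one-sided 5%) against 1.980 (two-sided 5%). Multiplied by 0.1936, these are observed differences of 0.321 and 0.384. Under the plan's effects, the chance of landing between the cut-offs is 9.6% (pooled) and 8.8% (90 vs 30 mg) at 40 per arm, and 9.7% and 10.6% at 33 per arm.

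**Aim 2.** Take pooled baclofen by stratum, with c per cell. SE = √(2 × (1/c + 1/(2c))) = √(3/c).

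- c = 20: ncp = 1.2/0.3873 = 3.098, df 114. A 1-df test at two-sided 5% gives 86.70% (printed 86.7%); at one-sided 5%, 92.4%.
- c = 16.76 (33.52 per arm): ncp = 2.836. Two-sided 5% gives 80.16% (printed 80.2%); one-sided 5%, 87.9%.
- c = 16.5 (33 per arm): two-sided 5% gives 79.5%.

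The alternative is a 2-df interaction F test with the effect of 1.2 in both dose arms. At 10% it gives 86.9% at c = 20, 80.1% at c = 16.5 and 80.7% at c = 16.76. At 5% it gives 78.7%, 69.8% and 70.5%.

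**The case against.** A reader might infer that the plan certainly applies one rule to Aims 1 and 3 and another to Aim 2. The documents do not establish that. The mixed reading matches Aim 2 exactly at full sample size, but after attrition it needs 33 per arm for Aim 1 and 33.52 for Aim 2. With 33 per arm throughout, it gives 79.5% for Aim 2 against the printed 80.2%, whereas a single 10% level with a 2-df interaction gives 86.9% and 80.1% against 86.7% and 80.2%. A three-level treatment factor also has a 2-df interaction by default. Neither reading is proven.

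A reader might also infer that the printed powers are miscalculated. They are not: Aims 1 and 3 are correct at one-sided 5%, a rule that a Phase II trial with directional hypotheses could declare. But directional wording of a hypothesis does not declare a one-sided test.

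Nor is the trial shown to be underpowered for everything. At two-sided 5%, 90 mg against placebo (d 0.8) has 94.4% power at 40 per arm, and the omnibus test has 91.9%. Section 7.2 also brings the pre-treatment drinking measure into the models and says the repeated-measures analysis has more power. If that covariate correlated 0.45 with outcome (an assumption; the documents give no value), two-sided power would return to 81.8% and 84.6% at 40 per arm; with no correlation it stays at 72.6% and 75.8%. All of this is fair, but 7.1 bases its powers on the summary scores and prints none for these other analyses.

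**Conclusion.** The omission is plain, and it affects the primary analysis. The printed Aim 1 and Aim 3 powers require an undeclared one-sided 5% (or two-sided 10%) rule. Under the customary two-sided 5% they are overstated by about 9 to 11 points: 72.6% and 75.8% at 40 per arm, 72.4% and 67.5% at 33 per arm, and 72.6% and 72.4% for Aim 3. Under the plan's assumed effects, for any one of these contrasts, about one trial in ten would give a result whose significance depends on the unstated rule.

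These figures assume the plan's own effect sizes and unadjusted summary-score contrasts with variance pooled over three arms. That Aim 2 follows a different convention is the better fit but only an inference, and the finding does not depend on it.

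**What to change.** Before the data are analysed, state alpha and sidedness for each aim in 7.1 and 7.2, and recompute all powers on that basis with one attrition rounding (33 or 33.52 per arm) for every aim.

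- **If two-sided 5% is used:** restate Aim 1 as 72.6% and 75.8% at 40 per arm, and 72.4% and 67.5% at 33 per arm (73.1% and 68.2% at 33.52). Restate Aim 3 as 72.6%, and 72.4% at 33 per arm (73.1% at 33.52). Name the degrees of freedom of the Aim 2 test and print its power to match. A 1-df test has 86.7%, then 79.5% at 33 per arm or 80.2% at 33.52. A 2-df test has 78.7%, then 69.8% or 70.5%. Qualify the power statements in the closing paragraph of the Abstract with the test and its power.
- **If one-sided 5% or two-sided 10% was intended for Aims 1 and 3:** declare and justify it, and state the Aim 2 rule separately.
- **If the omnibus, covariate-adjusted or repeated-measures model is meant to carry the power claim:** say so, and print its power and assumptions.

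The cost is protocol wording only, with no extra patients. The downside is either a less favourable stated power or the need to justify a one-sided (or 10%) test.

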## 7.2 Statistical Methods

**Specific Aim 1. To test the hypothesis that baclofen, 30 mg/d and 90 mg/d, is well tolerated and superior to placebo in enhancing abstinence and reducing heavy drinking days in alcohol dependence and that 90 mg/d is superior to 30 mg/d.**

Summary measures of the proportion of abstinence days/heavy drinking days will be derived from the TLFB for the entire medication period. We will derive weekly drinking measures from TLFB as well to provide information on the impact of time on usage. Descriptive statistics and exploratory graphing will be used to assess the distribution of the data and the need for transformations. In the case of %ABS/%HDD, the arc-sine transformation is quite commonly used.

**Primary Efficacy Analysis:** For the Summary measure, we will fit a general linear model on the outcome variable, consisting of main effect for treatment status. Goodness-of-fit, will be analyzed for outliers and influential observations. While these summary measure approaches are simple to implement and commonly used, information concerning the effect of time on the treatment effect is ignored. To understand the impact of time we will also conduct a repeated measures models analysis. From the weekly usage measures we will fit a mixed effects model consisting of main effect for treatment status. This repeated measures approach provides more information about the effect of treatment over time and therefore, more power compared to summary analyses above. We will also include the interaction of time and treatment. The interaction of time and treatment will answer the question as to whether the treatment effect is consistent over the entire treatment period or varies over the weeks. The mixed effects framework offers flexibility for the outcomes, e.g. any usage versus none, or count outcome data, e.g. number of abstinent days (Wolfinger and O'Connell, 1993). Appropriate covariance structure will be determined based on the AIC (Akaike Information Criteria) and BIC (Bayesian Information Criteria). We will evaluate the baclofen effect for changes in CDT using the mixed model approach described above. Within all framework, statistical contrasts will allow us to compare the two levels of BAC to PBO, as well as statistically contrasting the two levels of BAC. The advantage of the statistical contrasts is it allows us to use all available data to estimate the variance (variance-covariance for the repeated measures) of the outcome, while also properly distributing the degrees of freedom for the analytical test to account for the three levels of treatment.

**Treatment of Missing Data:** With repeated assessments, missing data/attrition is inevitable, but the key thing is that the specified contrasts are not affected due to the presence/absence of data. We will use pattern-mixture models to assess if there is bias due to drop out or missing data (Hedeker and Gibbons, 1997). To address missing data in the survival models, Dupuy and Mesbah(2004) considered jointly modeling time to event data with missing covariate data in order to assess if the missing data is ignorable or non-ignorable. These approaches will be implemented to the fitted cox model. Days in treatment may directly impact the treatment comparison for assessing differences. To control for this potential issue, we will also assess Marginal Structural Cox Regression models (Xiao et al., 2010).

**Adjustment for Covariates:** All modeling approaches allow for the inclusion of covariates. We will include any measures differing at baseline or important potentially confounding measures (i.e. gender, race) in our models to disentangle the intervention effect from these measures

**Specific Aim 2. To test the hypothesis that a history of heavy drinking as assessed by average drinks/drinking day in the 30 days preceding screening predicts baclofen response in alcohol dependence.**

We will include the pre-treatment HDD measure in all models above to examine its predictive merit, as well as its potential moderating impact of the baclofen effect. Moderation effect will be assessed by including the interaction of pre-treatment HDD with the treatment assignment. We will treat pre-

treatment HDD as a continuous measure. We will use mean profile plots based on quartiles of HDD to assess if the continuous measure has a linear, piecewise linear, or curvilinear effect. .

**Specific Aim 3. To test the hypothesis that baclofen, 30 mg/d and 90 mg/d, is superior to placebo in reducing anxiety in alcohol dependence.**

Our analytic procedure is as described in Aim 1 using mixed effects model to account for the repeated measures over time, while contrasting the mean intervention effect as well as assessing the potential moderation effect of pre-treatment HDD.

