In summary, the present proposal is innovative and of clinical significance as it will test and compare standard and high-dose baclofen for efficacy and safety in individuals with AD. The proposal is adequately powered to test the primary hypothesis and provides good power to assess whether drinks/drinking day is predictive of baclofen response. Adequate power is also present to examine the anxiolytic effect of baclofen. Ascertaining the effects of standard and high-dose baclofen, the predictive value of heavy drinking on baclofen response and the anxiolytic effect of baclofen are important goals towards determining whether baclofen has true value for the clinical management of the patient with alcohol dependence.

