## **2 Study Objectives**

Primary :

- To test the efficacy and safety of 30 mg/d and 90 mg/d of baclofen compared to placebo for individuals with alcohol dependence.

Secondary:

- To test the hypothesis that a history of heavy drinking as assessed by average drinks/drinking day in the 30 days preceding screening predicts baclofen response in alcohol dependence.
- To test the hypothesis that baclofen, 30 mg/d and 90 mg/d, is superior to placebo in reducing anxiety in alcohol dependence.

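### Section 7.1 gives no power for either dose against placebo, the comparison the primary objective names; at its own d = 0.2, 30 mg has 14–23%, and its Aim 1 figures do not hold at two-sided 0.05

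*Combined protocol and SAP*

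**What the plan says.** The primary objective in section 2 is "To test the efficacy and safety of 30 mg/d and 90 mg/d of baclofen compared to placebo". Aim 1 in section 7.2 hypothesises that "baclofen, 30 mg/d and 90 mg/d, is well tolerated and superior to placebo in enhancing abstinence and reducing heavy drinking days", and adds that the higher dose beats the lower. The Primary Efficacy Analysis says that "statistical contrasts will allow us to compare the two levels of BAC to PBO, as well as statistically contrasting the two levels of BAC".

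Section 7.1 assumes Cohen's d = 0.2 "for the contrast between PBO and 30mg coupled with a large effect size" (d = 0.8) for placebo against 90 mg. From these it reports "82.2% power with 120 participants (40/arm) in testing the overall baclofen effect as well as 84.7% power to contrast 30 mg to 90 mg". For 16.2% attrition it says that "a slightly larger effect size would be required to provide sufficient power for the overall BAC effect", raises the average effect to 0.55, and quotes 82.0% for the overall effect and 78.1% for dose against dose at d = 0.6. Aim 2 is given 86.7%, or 80.2% with attrition. Aim 3 repeats 82.2% and 82.0%.

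The Abstract concludes: "The proposal is adequately powered to test the primary hypothesis". The documents state no significance level, no sidedness and no rule for when Aim 1 is met.

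**The concern.** The objective and Aim 1 name two dose–placebo comparisons, and 7.1 gives power for neither. The assumed 30 mg effect is small, so that comparison is the weak one, yet the Abstract's assurance carries no qualification.

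Three things are at stake. A reader may take a non-significant 30 mg result as evidence of no effect. A reader may take a significant pooled result as support for 30 mg when the 90 mg arm alone produced it. And with no stated alpha, the reader cannot tell that the quoted Aim 1 powers depend on a level laxer than two-sided 0.05.

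**Working it through.** **Inputs (section 7.1).** 40 per arm. d = 0.2 for 30 mg and 0.8 for 90 mg against placebo. The dose difference is 0.8 − 0.2 = 0.6. The pooled effect is (0.2 + 0.8)/2 = 0.5, which is also the value given for Aim 3. Attrition is 16.2%: 40 × 0.838 = 33.5, taken as 33 per arm because that reproduces the plan. Alpha is not stated, so three levels are shown.

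**Method.** Noncentral t on the summary score that 7.1 powers, with the SD pooled over three arms. Error df = 3n − 3 (117 at 40 per arm, 96 at 33). Noncentrality (ncp) = d / √(1/n₁ + 1/n₂).

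**Step 1: reproduce the plan's Aim 1 figures (power, %).**

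| Contrast | n/arm | d | ncp | 2-sided 0.05 | 1-sided 0.05 | 2-sided 0.10 | Stated |
|---|---|---|---|---|---|---|---|
| Pooled vs placebo | 40 | 0.5 | 0.5/√(1/40+1/80) = 2.582 | 72.6 | 82.2 | 82.2 | 82.2 |
| 90 vs 30 mg | 40 | 0.6 | 0.6/√(2/40) = 2.683 | 75.8 | 84.7 | 84.7 | 84.7 |
| Pooled vs placebo | 33 | 0.55 | 0.55/√(1/33+1/66) = 2.580 | 72.4 | 82.0 | 82.0 | 82.0 |
| 90 vs 30 mg | 33 | 0.6 | 0.6/√(2/33) = 2.437 | 67.5 | 78.1 | 78.1 | 78.1 |

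All four match to the decimal at one-sided 0.05 and equally at two-sided 0.10. None matches at two-sided 0.05. With attrition and the pooled effect left at 0.5, power is 64.1 / 75.3 / 75.3%.

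**Step 2: the contrasts 7.1 leaves out, by the same method (power, %).**

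| Contrast | n/arm | d | ncp | 2-sided 0.05 | 1-sided 0.05 | 2-sided 0.10 |
|---|---|---|---|---|---|---|
| 30 mg vs placebo | 40 | 0.2 | 0.894 | 14.4 | 22.5 | 23.1 |
| 30 mg vs placebo | 33 | 0.2 | 0.812 | 12.7 | 20.1 | 20.8 |
| 90 mg vs placebo | 40 | 0.8 | 3.578 | 94.4 | 97.2 | 97.2 |
| 90 mg vs placebo | 33 | 0.8 | 3.250 | 89.6 | 94.3 | 94.3 |

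The plan's attrition case (average 0.55, difference 0.6) implies d = 0.55 − 0.30 = 0.25 for 30 mg. Power is then 17.1 / 26.2 / 26.6% at 33 per arm.

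**Step 3: which level Aim 2 uses.** Inputs: effect 1.2 in heavy drinkers and 0 in the others, 20 per cell, doses pooled. SE = √[2(1/20 + 1/40)] = √0.15 = 0.387; ncp = 1.2/0.387 = 3.098; df = 114. Power is 86.7% at two-sided 0.05 (stated 86.7%) and 92.4% at two-sided 0.10. With 20 × 0.838 = 16.76 per cell, ncp = 2.836 and power is 80.2% (stated 80.2%) against 87.9%. Rounding to 16.5 per cell gives 79.5%. A 2-df interaction test with both doses at 1.2 has the same noncentrality (3.098² = 9.6). At 0.10 it gives 86.9% and, at 16.76 per cell, 80.7%: close, but not a match. The natural reading is that Aim 2 is at two-sided 0.05 and Aim 1 is not.

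**Step 4: consequences at 40 per arm.**
- Both doses beat placebo under the plan's effects (1,000,000 simulated trials): 14.3% at two-sided 0.05, 22.9% at two-sided 0.10.
- All three parts of Aim 1 on one outcome, including 90 mg over 30 mg: 6.7% and 14.9%.
- 30 mg inert and 90 mg at d = 0.8: pooled d = 0.4, ncp = 0.4/√(1/40+1/80) = 2.066. The pooled test is significant in 53.5% of trials at two-sided 0.05 and 65.9% at two-sided 0.10.

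**The case against.** The strongest reply is that the overall baclofen effect is the primary hypothesis. Section 7.1 powers exactly two contrasts, pooled against placebo and dose against dose, and these form an orthogonal pair for three arms. The contrast sentence in 7.2 can be read as that pair, and Aim 3 speaks of "while contrasting the mean intervention effect as well as assessing the potential moderation effect of pre-treatment HDD". On this reading the Abstract and 7.1 agree. This stands as a possible reading, so the documents do not support a flat statement that the adequacy claim is false. But section 2 and the Aim 1 hypothesis name both doses and nowhere make the overall effect primary.

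Leaving a small effect unpowered is also legitimate in a 120-patient Phase II trial, and d = 0.2 is the low end: 7.1 describes the earlier 30 mg finding as small to medium. At d = 0.35 power would be 34% (two-sided 0.05) or 47% (two-sided 0.10), and at d = 0.5 it would be 60% or 72%. All remain under 80%, and 0.2 is the value the plan adopted. The issue is disclosure.

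The plan says the mixed model has more power than the summary analysis. It gives no correlation from which to compute a gain, and 7.1 rests on the summary scores.

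Two stronger inferences are tempting. A reader might compute a false-positive rate of about 12% from three ungated contrasts. That counts results in the wrong direction; in the hypothesised direction it is 6.5% (two-sided 0.05, one outcome), and the plan nowhere says that any single win suffices. A reader might also take 14–23% as the chance of meeting Aim 1. That range is for both doses beating placebo; Aim 1 as written also needs 90 mg over 30 mg, which gives about 7–15%.

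**Conclusion.** The point holds as a reporting and specification defect. The 30 mg comparison named in the objective has 14.4–23.1% power at the plan's own effect size (12.7–20.8% at 33 per arm), and this is not disclosed. The claim of adequate power does not hold if each dose must beat placebo, and it fits 7.1 only if the overall effect is primary, which the plan must then say.

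Separately, 7.1 appears to mix significance levels. At two-sided 0.05, the level that reproduces Aim 2, every stated Aim 1 power falls below 80%, and of the four contrasts only 90 mg against placebo exceeds it.

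It does not follow that the trial as a whole is underpowered: 90 mg against placebo has 94–97% at 40 per arm if d = 0.8 is right. The figures assume the plan's effect sizes, equal arms, and an unadjusted analysis of the summary score. The mixing of levels is inferred from reproduction, since no level is written down.

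**What to change.** 1. Section 7.1: state one alpha and sidedness for all aims. If it is two-sided 0.05, replace 82.2, 84.7, 82.0 and 78.1% for Aim 1 with 72.6, 75.8, 72.4 and 67.5%, and change 82.2 and 82.0% for Aim 3 to 72.6 and 72.4%.
2. Section 7.1: add power for 30 mg and for 90 mg against placebo on that basis, with and without attrition at unchanged effect sizes.
3. Abstract: limit the adequacy claim to the contrasts that meet it. Say that a non-significant 30 mg result is not evidence of no effect, and that a pooled win is not evidence for 30 mg.
4. Section 2 and Aim 1 in 7.2: say which result is primary.
   - Overall effect: a win then supports no claim for 30 mg alone.
   - Both doses required: no adjustment between them, but success is about 14–23% at the plan's effects.
   - Either dose sufficient: control error over the two dose–placebo contrasts, by fixed sequence, Holm or Dunnett. Testing 90 mg first in sequence keeps its full power, but 30 mg is then tested only after a 90 mg win. Holm lowers 90 mg against placebo from 94.4 to 90.3% at two-sided 0.05.

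The cost is protocol and SAP wording and less favourable stated power. No additional patients are needed.
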